8.5 UNANTICIPATED PROBLEMS

8.5.1 Definition of Unanticipated Problems (UP)

Any incident, experience, or outcome that meets **all** of the following criteria:

- Unexpected in terms of nature, severity, or frequency given (a) the research procedures that are described in the protocol-related documents, such as the IRB-approved research protocol and informed consent document; and (b) the characteristics of the participant population being studied; and
- Related or possibly related to participation in the research (“possibly related” means there is a reasonable possibility that the incident, experience, or outcome may have been caused by the procedures involved in the research); and
- Suggests that the research places participants or others (which many include research staff, family members or other individuals not directly participating in the research) at a

greater risk of harm (including physical, psychological, economic, or social harm) than was previously known or expected.

8.5.2 Unanticipated Problem Reporting

The investigator will report UPs to the NIH IRB as per HRPP Policy 801.

9 STATISTICAL CONSIDERATIONS

9.1 STATISTICAL HYPOTHESIS

BSS will cause a change in the relative abundance of certain bacterial taxa approximately 1 month post-BSS compared to baseline (pre-BSS). We expect there to be a decrease in beneficial bacterial taxa (eg, *Lactobacillus*) and increase in potential pathobionts (eg, *Enterococcus*). This will be most pronounced at day 2 (the day after therapy) and some changes may persist up to 1 month. This hypothesis is based on our findings in murine models (section 2.2.).

9.2 SAMPLE SIZE DETERMINATION

In our laboratory studies (section 2.2), on the day after BSS treatment, the average fold reduction of *Lactobacillus* reads pre- and post-BSS use was 1.57 and the standard deviation (SD) was 0.94. Given the possible larger individual variability and potential overall lower abundance of *Lactobacillus* in humans, for the range of SD between 0.5 to 3, Table 1 below gives the sample size and power calculation to detect a 2-log₁₀ decrease of *Lactobacillus* reads pre- and post-BSS use for type one error of 0.05.

Table 1: Sample size and power calculation

SD	0.5	1	1.5	2	2.5	3
N=20	100%	99.9%	98%	87%	69%	54%
N=15	100%	99.9%	94%	75%	56%	42%

With 20 healthy volunteers, this study has a power 87% to detect the 2-fold change if the standard deviation is 2.

At the end of the study, for the primary endpoint, a paired t-test will be used to calculate the mean log₁₀ change at each post-treatment time point compared to baseline and the 95% confidence interval will be provided. More sophisticated statistics will also be used for the overall microbiome data (section 9.4.2).

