3 OBJECTIVES AND ENDPOINTS

OBJECTIVES	ENDPOINTS	JUSTIFICATION FOR ENDPOINTS
Primary		
To evaluate the effect of BSS on the human gut microbiome.	Differences in the relative abundance of taxa in stool samples pre-BSS and approximately 1 month post-BSS. Differences in microbiome metrics of alpha diversity and beta diversity will also be assessed.	Hypothesis: there will be a decrease in beneficial bacterial taxa (eg, Lactobacillus) and increase in potential pathobionts (eg, Enterococcus). This will be most pronounced at day 2 (the day after therapy) and some changes may persist up to 1 month. This hypothesis is based on our findings in murine models (section 2.2.). These specific endpoints of relative abundance of taxa, alpha diversity, and beta diversity were chosen as they are standard metrics to assess changes in the microbiome.(28, 29)

OBJECTIVES	ENDPOINTS	JUSTIFICATION FOR ENDPOINTS
Secondary		
To evaluate the effect of BSS on the human gut metabolome.	Differences in the stool metabolome (including short chain fatty acids, bile acids, and untargeted metabolomics) pre-BSS and approximately 1 month post-BSS.	Hypothesis: there will be a change in specific stool metabolites (eg, a decrease in protective secondary bile acids and short chain fatty acids) with BSS therapy. This will correlate with gut microbiome changes. Stool metabolites are produced by gut microbiota and also contain host products. Importantly, they can assess the function of the microbiota, ie, “what are they doing” rather than just “what’s there.”(30) Moreover, bacterial metabolites have a key role in gut barrier function, host immunity, and inflammation, which is important in this study when assessing microbiome and host responses to BSS.(31) Targeted assays for metabolites of special interest, such as bile acids, short chain acids, and sulfides may be performed.(32, 33) Wide targeted or untargeted metabolite assays will also be performed to uncover other metabolites of relevance.
Tertiary/Exploratory		

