7.2 PARTICIPANT DISCONTINUATION/WITHDRAWAL FROM THE STUDY

An individual participant will be withdrawn from the study for any of the following:

- An individual participant's decision. (The investigator should attempt to determine the reason for the participant's decision.)
- Non-compliance with study procedures to the extent that it is potentially harmful to the participant or to the integrity of the study data. For example, the participant does not complete the full BSS regimen.
- Participant is unable to provide ongoing informed consent.
- The participant becomes pregnant before day 0.
- The investigator determines that continued participation in the study would not be in the best interest of the participant.

Participants who withdraw or are withdrawn from the study prior to day 14 will be replaced. If a participant is replaced, then all the data collected from that participant will still be included for the safety assessment.

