8.2.1 Biospecimen Evaluations

Stool: Stool is the only required sample and will be collected at all study visits. For remote visits, participants will be provided with an at-home collection kit, which they can ship to the NIH. Participants may not be able to provide a stool sample at all visits. The minimum number of samples required for this study (ie, that does not constitute a protocol deviation, section 10.9) is 1 sample before starting the BSS regimen and 1 sample after completion of the regimen. Research evaluations on stool samples will include the following:

- Microbiome sequencing (including 16S ribosomal [r]RNA gene sequencing, shotgun metagenomic sequencing and evaluation of the resistome, virome, and parasitome).
- Metabolomics to evaluate intestinal metabolomic profiles, and when combined with microbiome/metagenomic studies, may suggest some functional role for candidate microbes of interest.
- Fecal flow (sorting and 16S and/or shotgun sequencing of immunoglobulin [Ig]A-bound organisms, which is an indication of pathogenicity).
- Lipocalin, calprotectin, and α -1-anti-trypsin levels (to evaluate mucosal inflammation and malabsorption).
- Measurement of secreted IgA and antimicrobial peptides.
- Culturing/polymerase chain reaction for specific organisms.
- Stool proteomics.
- Use of stool samples in murine models.
- Metatranscriptomics (the gene expression of the microbiota and host).
- Storage for future research.

Blood: Blood is an optional sample that will only be collected at in-person visits. Between 30 to 150 mL of blood will be collected per visit. The amount of blood drawn for research purposes will be within the limits allowed for adult research participants by the NIH CC (Medical Administrative Policy 95-9, Guidelines for Limits of Blood Drawn for Research Purposes in the Clinical Center: <http://cc-internal.cc.nih.gov/policies/PDF/M95-9.pdf>). Research evaluations on blood include the following:

- Host immune and inflammatory responses, and specific responses to the microbiome.
- Metabolomics.
- Lipopolysaccharide and lipopolysaccharide-binding protein (for evaluation of bacterial translocation and intestinal permeability).

Abbreviated Title: BSS Gut Microbiome

Version Date: 05 July 2024

- Isolation and cryopreservation of peripheral blood mononuclear cells and serum (for the creation of induced pluripotent stem [iPS] cells and future evaluation of systemic immune responses).

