9.3 POPULATIONS FOR ANALYSES

To address the primary endpoint of a change in a relative abundance of bacterial taxa approximately 1 month post-BSS compared to baseline (pre-BSS), all participants with a stool sample for microbiome analysis at baseline and at least 1 stool sample for microbiome analysis after BSS treatment will be included.

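### The 87% power in section 9.2 rests on a day-after-treatment effect and is not shown to apply to the 1-month primary comparison, for which no rule secures a day 28 stool

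*Combined protocol and SAP*

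**What the plan says.** **Endpoint.** Section 3, and the synopsis in 1.1, define the primary endpoint as "Differences in the relative abundance of taxa in stool samples pre-BSS and approximately 1 month post-BSS". The hypothesis in 9.1 and the population statement in 9.3 name the same time point.

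**Power.** Section 9.2 reports that "on the day after BSS treatment, the average fold reduction of" *Lactobacillus* reads "was 1.57 and the standard deviation (SD) was 0.94", in the laboratory's mouse work. It then gives power for a 2-log10 fall at SDs from 0.5 to 3 with N=20 and N=15. The headline is 87% for N=20 and SD 2. The planned test is a paired t-test of each post-treatment visit against baseline. The background in 2.2.3 reports a fall of the same size, 2 logs, one day after treatment ended.

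**Expected time course.** Section 9.1 says: "This will be most pronounced at day 2 (the day after therapy) and some changes may persist up to 1 month".

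**Who supplies a 1-month sample.**
- Section 7.2: "Participants who withdraw or are withdrawn from the study prior to day 14 will be replaced". Nothing is said about later losses.
- Section 8.2.1: the least that avoids a protocol deviation "is 1 sample before starting the BSS regimen and 1 sample after completion of the regimen". It also accepts that some participants will not manage a stool at each visit.
- Section 9.3: for the 1-month endpoint, everyone with a baseline stool and "at least 1 stool sample for microbiome analysis after BSS treatment will be included".

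**The concern.** A power statement holds for one contrast, at one time point, with one test. Here the effect comes from the time when the plan expects the largest change, while the declared primary comparison comes about four weeks later, when the plan expects some of that change to have gone. A reader of 9.2 would take 87% as the power of the primary endpoint.

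The rules on participants do not secure that endpoint either. Someone who leaves at day 20, or who stays but never sends a day 28 stool, is not replaced. With one earlier post-BSS stool, that person still counts in the 1-month population. The number of pre versus 1-month pairs can thus fall below 20 without any rule noticing.

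The result is meant to inform a later randomized study (4.2). Without a stated day 28 sensitivity, readers cannot tell whether a null day 28 result reflects no lasting effect or a change too small for this study to detect.

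**Working it through.** **Inputs.** From 9.2: effect δ = 2 log10, SD σ = 0.5 to 3, N = 20 or 15, type I error 0.05. Sidedness is not stated; I take two-sided. For the paired test I take σ as the SD of the within-person change, which 9.2 does not specify.

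**Formulas.** Power is the probability that a noncentral t variable with noncentrality λ exceeds the two-sided 5% critical value in absolute size.
- Paired: λ = δ√n/σ, df = n − 1.
- Two-sample, n per group: λ = δ√(n/2)/σ, df = 2n − 2.

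**Step 1: reproduce Table 1 (δ = 2).**

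| | SD 0.5 | 1 | 1.5 | 2 | 2.5 | 3 |
|---|---|---|---|---|---|---|
| N=20 stated | 100% | 99.9% | 98% | 87% | 69% | 54% |
| two-sample, 20 per group | 100 | 100 | 98.4 | 86.9 | 69.3 | 53.8 |
| paired, 20 pairs | 100 | 100 | 100 | 98.9 | 92.4 | 80.7 |
| N=15 stated | 100% | 99.9% | 94% | 75% | 56% | 42% |
| two-sample, 15 per group | 100 | 100 | 94.1 | 75.3 | 56.2 | 42.2 |
| paired, 15 pairs | 100 | 100 | 99.8 | 94.9 | 82.1 | 67.1 |

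At N=20 and SD 2, the two-sample λ is 2 × √10 / 2 = 3.162 on 38 df (critical value 2.024), giving 86.9%. The paired λ is 2 × √20 / 2 = 4.472 on 19 df (critical value 2.093), giving 98.9%.

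The two-sample test matches all twelve cells within half a point. The planned paired test does not. Reading σ as a single-visit SD with no within-person correlation (change SD = σ√2) comes closer, at 85.1%, 67.0% and 51.6% for SD 2, 2.5 and 3 with N=20, but still misses the stated values.

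**Step 2: planned paired test at 1 month.** The text of 2.2.3 says that *Lactobacillus* differences were still significant at 30 days but gives no size, and 9.2 uses none. The effects below are therefore assumptions. SD of change is 2.

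| Assumed 1-month effect (log10) | λ at n=20 | Power, 20 pairs | Power, 15 pairs |
|---|---|---|---|
| 2.0 | 4.472 | 98.9% | 94.9% |
| 1.5 | 3.354 | 88.9% | 77.1% |
| 1.0 | 2.236 | 56.5% | 43.8% |
| 0.5 | 1.118 | 18.6% | 14.7% |

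The 15 pairs are also an assumption; the plan gives no loss rate.

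**Step 3: detectable change.** With 20 pairs, 80% power needs δ/σ = 0.660. That is 0.660 × 2 = 1.32 log10 at SD 2, or 0.660 × 3 = 1.98 log10 at SD 3.

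**Step 4: which uncertainty matters more.** At 20 pairs, halving the effect from 2.0 to 1.0 log10 takes power from 98.9% to 56.5%. Losing five pairs at 2.0 log10 takes it from 98.9% to 94.9%. At 1.0 log10 the same loss takes it from 56.5% to 43.8%. The unstated 1-month effect matters more than lost samples.

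**The case against.** The strongest reply is that the analysis is in practice per visit. Sections 9.2 and 9.4.2 compare each post-treatment visit with baseline, and 9.4.2 looks at how long a difference lasts once an early one is found. Under that sequence, sizing on the early effect and keeping anyone with one post-BSS stool is reasonable, and a day 2-only participant does inform the day 2 contrast. This stands as a defence of the wide analysis set for the other visits. It does not answer 9.3, which ties that set to the 1-month endpoint.

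A second reply is that lower power is partly disclosed. Power depends on δ/σ, so the SD 3 column of Table 1 is equivalent to an effect of 2 × 2/3 = 1.33 log10 at SD 2, and the N=15 row covers loss of a quarter of the sample. The numbers are there, but presented as between-person variability and sample size, not as fading of the effect by 1 month.

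Third, the gap in replacement is short. The day 14 window runs to day 21, where the day 28 window opens, and 7.3 asks staff to reschedule missed visits. This is fair for withdrawals, and it fits Step 4. It does not cover a participant who stays in the study without giving a day 28 stool.

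Finally, this is an exploratory pilot with confidence intervals planned at each visit. That lowers the severity; it does not make the stated power apply to the endpoint.

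**Conclusion.** The point holds as a mismatch between the power statement, the analysis set and the declared endpoint. The 87% is not shown to be the power of the 1-month comparison, and no rule secures the day 28 stool on which that comparison depends.

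The documents do not support two stronger readings. A reader might infer that the study is underpowered at 1 month. That is not established: if 2 log10 persisted, paired power would be 98.9%, and at 1.5 log10 it would still be 88.9%, above the stated figure. Power falls below 80% only if the residual effect is under 1.32 log10 (20 pairs, SD of change 2), and the text gives no 30-day size to judge that by. Figure 1C may, but 9.2 does not draw on it. A reader might also infer that Table 1 is simply the power of the day 2 contrast. It is not, because its values match a two-sample test, not the planned paired one. Table 1 itself names no time point; the link to the day after treatment comes from the sentence before it and from 2.2.3.

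These figures assume a two-sided 0.05 test and an SD of the paired change equal to the SD in 9.2. The 1-month effects and the loss to 15 pairs are illustrations. Severity: should be fixed, given the exploratory single-arm design.

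**What to change.** - **Section 9.2.** Recompute the table with the planned paired t-test, and say that σ is the SD of the within-person change. State that the 2-log10 effect is a day-after-treatment effect. Add day 28 power over a range of residual effects (for example 0.5, 1.0, 1.5 and 2.0 log10) or the change detectable with 80% power (1.32 log10 at SD 2, 1.98 at SD 3). Do not relabel the existing Table 1 as day 2 power.
- **Section 9.3.** Base the 1-month contrast on participants with a pre-BSS stool and a day 28 (±7) stool, and keep the any-post-sample set for the other visits. Alternatively, estimate the day 28 contrast from a mixed model using all visits.
- **Section 7.2.** Extend replacement to participants without a day 28 stool, within the accrual ceiling of 40.

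The cost is protocol wording, a stated day 28 power that falls if the effect fades, and perhaps a few more participants. At an assumed loss of 10% to 20%, keeping 20 day 28 pairs takes 20/0.9 = 22.2, so 23, to 20/0.8 = 25 enrolled. The change should be made before the outcome data are examined.

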2.2.2 Bismuth Subsalicylate: Mechanism of Action

[figure not shown]
The mechanism of action of BSS is not fully understood. BSS exhibits both antisecretory and antimicrobial actions. In the stomach, it hydrolyzes into two compounds: bismuth and salicylic acid. The salicylate compound is almost completely absorbed into the bloodstream, while bismuth salt is minimally absorbed.(7) The bismuth salts contain bactericidal and antimicrobial activity, and prevent bacteria from binding and growing on the mucosal cells. Additionally, antisecretory effects are most likely due to 1) the reduction in prostaglandin formation, as BSS

inhibits cyclooxygenase (prostaglandin induces inflammation and hypermotility) and 2) the stimulation of reabsorption of fluids, sodium, and chloride (this action helps decrease fluid loss).(8) Importantly for this current study, BSS also sequesters local gut sulfides, with sulfides being produced by host cells and microbes.(9) Sulfide, an inhibitor of cellular respiration, is important for resistance to host colonization by pathogens.(9)

2.2.3 Bismuth Subsalicylate: Effect on the Gut Microbiome and Host Response in Murine Models

LHIM recently described for the first time that BSS affected the gut microbiome of mice through the mechanism of sequestering local gut sulfides, with a large increase in *Enterococcus*, after treatment with a high-dose regimen.(9) Building on this work, we then designed another mouse model of BSS treatment with doses scaled down to a mouse volume from those recommended in humans (rather than higher dose). Mice were gavaged with 5 mg of BSS in a 200- μ L solution every 12 hours for 72 hours. This treatment substantially altered the microbiome composition. One day after the end of treatment, we noted a 2-log decrease in *Lactobacillus* genus abundance by 16S reads, a 3-log increase in *Enterococcus* abundance (Figure 1A-B), and a 1-log increase in *Akkermansia* abundance. Longitudinally, we observed alterations in the microbiome out to 30 days post treatment, with significant differences persisting for *Lactobacillus* (Figure 1C) (unpublished data, manuscript in preparation). Beta diversity (weighted unifracs distance) of control and treated animals are shown in Figure 1D-E for 1 and 30 days after the end of treatment, respectively.

[figure not shown]
Figure 1: Changes in mouse fecal microbiome after bismuth subsalicylate treatment

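### Section 9.2 gives 87% as the power for a 2-fold change, but the figure belongs to a 2-log10 (100-fold) decrease; the unit of the mouse value and the basis of Table 1 also need stating

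*Combined protocol and SAP*

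**What the plan says.** Section 9.2 starts from the laboratory mouse data. On the day after treatment, the reduction in *Lactobacillus* "reads pre- and post-BSS use was 1.57 and the standard deviation (SD) was 0.94". The section calls this a fold reduction and gives no log unit. It expects humans to vary more and perhaps to carry less *Lactobacillus*, so it tabulates power "for the range of SD between 0.5 to 3".

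The effect behind Table 1 is explicit: the table is to "detect a 2-log₁₀ decrease of *Lactobacillus* reads pre- and post-BSS use for type one error of 0.05". The N=20 row reads 100, 99.9, 98, 87, 69 and 54% for SD 0.5, 1, 1.5, 2, 2.5 and 3. The N=15 row reads 100, 99.9, 94, 75, 56 and 42%. The sentence after the table then says: "With 20 healthy volunteers, this study has a power 87% to detect the 2-fold change if the standard deviation is 2".

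The analysis named at the end of the section is a paired t-test on the mean log10 change from baseline. Section 2.2.3 describes the mouse result one day after the end of treatment in other terms: "we noted a 2-log decrease in" *Lactobacillus* abundance.

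**The concern.** The table and the sentence that summarises it name different effects. A 2-log10 decrease is 100-fold; a 2-fold change is a halving or doubling. The two differ by a factor of 50, and one power figure cannot serve both.

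The 87% sentence is the only statement in section 9.2 that ties N=20 to a capability, so it is the one likely to be quoted later. Taken literally, it says that 20 volunteers would usually reveal a halving of *Lactobacillus* even at SD 2. A null result could then be read as evidence against a 2-fold change. Section 4.2 makes further randomised work depend on whether an effect is seen, so that misreading has a consequence.

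The mouse input has a related problem. A literal 1.57-fold reduction is far smaller than a 2-log decrease. If 1.57 is in log10 units, it is close to the figure in section 2.2.3 but below the design target. The text does not say which is meant.

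**Working it through.** **Inputs.** All are from section 9.2 unless noted: N=20 (also 15); SD 2 (range 0.5 to 3); type I error 0.05; Table 1 effect 2 log10; effect in the sentence 2-fold; mouse value 1.57 with SD 0.94; mouse effect in section 2.2.3, 2-log. Not stated: whether the test is two-sided, and whether the SD is that of the within-person change or of a single measurement. I assume two-sided and show where the other choices matter.

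**Formulas.** Power comes from the noncentral t distribution.
- Paired: df = n − 1, noncentrality = (δ/SD)·√n, with SD that of the change.
- Two-sample: df = 2n − 2, noncentrality = (δ/SD)·√(n/2), with n per group.

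**Step 1: reproduce 87%.** Take δ = 2 log10, SD = 2, n = 20, so δ/SD = 1.
- Two-sample: noncentrality √10 = 3.16, df 38, power 86.9%. This matches.
- Paired: noncentrality √20 = 4.47, df 19, power 98.9%. This does not match.

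The two-sample formula also reproduces the other informative cells:

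| | SD 1.5 | SD 2 | SD 2.5 | SD 3 |
|---|---|---|---|---|
| N=20, Table 1 | 98% | 87% | 69% | 54% |
| N=20, two-sample | 98.4% | 86.9% | 69.3% | 53.8% |
| N=15, Table 1 | 94% | 75% | 56% | 42% |
| N=15, two-sample | 94.1% | 75.3% | 56.2% | 42.2% |

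A paired test with SD of the change equal to √2 × SD (two uncorrelated measurements) gives 85.1% at N=20, SD 2 and 72.2% at N=15, SD 2. That is near the table but does not match it. So the 87% belongs to a 2-log10 effect, calculated as for two independent groups of 20.

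**Step 2: power for a literal 2-fold change.** δ = log10(2) = 0.301; δ/SD = 0.301/2 = 0.151.
- Paired, two-sided: 9.8%. Paired, one-sided: 16.0%.
- Two-sample, two-sided: 7.5%.

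Changing the log base does not rescue the sentence. In log2 units a 2-fold change is 1, and at SD 2 the two-sided power is 56.5% paired or 33.8% two-sample. In natural logs it is 0.693, giving 31.3% or 18.8%.

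Power for a 2-fold change depends strongly on the SD. With the paired test it is 27.5% at the mouse SD of 0.94 and 72% at SD 0.5.

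**Step 3: the mouse value.**
- Read as a literal fold: log10(1.57) = 0.196, far from 2-log.
- Read as log10: 10^1.57 = 37-fold, below the 100-fold target. Power at SD 2, N=20 is then 91.4% paired or 67.7% two-sample.

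**Step 4: Table 1 on the planned test**, taking the SD as that of the change, N=20, δ = 2 log10: 98.9% at SD 2, 92.4% at SD 2.5, 80.7% at SD 3.

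**Step 5: minimum detectable change at 80% power, N=20.** Solving the paired power equation gives δ/SD = 0.660.

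| SD of change | log10 change | Fold |
|---|---|---|
| 0.5 | 0.33 | 2.1 |
| 1 | 0.66 | 4.6 |
| 2 | 1.32 | 21 |

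By the two-sample method, the SD 2 entry would be 1.82 log10, about 66-fold.

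**The case against.** The strongest reply is that the sentence contains a slip of unit and the calculation behind it is intact. It restates a cell of a table whose 2-log10 target is given just above, and the planned analysis is on log10 change. No other section commits the study to detecting a halving. The study is exploratory, and section 9.2 promises 95% confidence intervals, which will show directly which changes the data exclude. All of this stands. It explains the error and limits its harm, but does not make the sentence true.

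A reader might go further in three ways that the documents do not support.

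- *The target exceeds the mouse effect.* Section 2.2.3 reports a 2-log decrease, equal to the target. Only the 1.57 figure falls short, if it is log10, and that unit is inferred. What is supportable is that the two figures need reconciling.
- *The design can detect only changes of tens of fold.* That is so at SD 2, but not at SD 1 (4.6-fold) or SD 0.5 (2.1-fold), both within the range that Table 1 covers.
- *Correcting the section makes the study look weaker.* If the SD is that of the change, the planned test has 98.9% power for 2 log10 at SD 2, and 91.4% even for 1.57 log10. Both exceed the stated 87%.

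**Conclusion.** The power statement is wrong as written. The 87% is for a 100-fold decrease. For a literal 2-fold change at N=20 and SD 2 the power is about 10% with the planned test, and 7.5% to 16.0% over the variants tried on the log10 scale. The 10% assumes a two-sided test and that SD 2 is the SD of the within-person log10 change.

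The low figure should not be read as showing that the study is underpowered for its intended target. The probable intention was 2-log10, and for that effect Table 1 is conservative if its SD is that of the change. Two points remain after the wording is corrected. The unit of 1.57 is unstated and the value is unreconciled with section 2.2.3. Table 1 also reproduces as a two-sample calculation, while the plan is a paired test.

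**What to change.** In section 9.2:

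1. Replace 2-fold by 2-log10 (100-fold) in the concluding sentence, and make no claim of 87% power for a 2-fold change.
2. Check the mouse data, state the unit of 1.57, and reconcile it with the 2-log decrease in section 2.2.3.
3. State whether the SD is that of the within-person log10 change, and whether the test is two-sided.
4. Recompute Table 1 for the planned paired t-test on that definition, and quote the recomputed cell in place of 87%. If the SD is that of the change, the values in Step 4 apply. If 1.57 proves to be log10, add a row for it (91.4% at SD 2).
5. Give the minimum detectable change at 80% power by SD on the same basis, as in Step 5. Setting the paired 21-fold figure beside the present table would mix two methods.

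The cost is wording, one recomputed table and a check of existing laboratory data. Sample size, endpoint and test are unchanged.

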4.2 SCIENTIFIC RATIONALE FOR STUDY DESIGN

In our murine models, BSS caused a profound effect in the gut microbiome with subsequent changes in the host response. As there are no data on the effect of BSS on the human gut microbiome, an open-label pilot study is needed to gather preliminary data. The study design is strengthened by comparing the microbiome within a same individual before and after intervention as previously reported in other studies of the gut microbiome.(37) Moreover, in our murine models, longitudinal microbiome changes were seen within individual mice, in addition to between control and treatment groups. If an effect is seen, this lays the foundation for confirmation in a study with a randomized control design and further studies to assess the clinical impact and potential health outcomes of these changes in humans.

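### Section 9.2 names a paired t-test, but the informative cells of Table 1, including the 87%, are those of an unpaired two-group test with N per group; if SD means SD of change, power is understated

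*Combined protocol and SAP*

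**What the plan says.** Section 9.2 (Sample Size Determination) starts from mouse data: "the average fold reduction of *Lactobacillus* reads pre- and post-BSS use was 1.57 and the standard deviation (SD) was 0.94". It then states that "Table 1 below gives the sample size and power calculation to detect a 2-log₁₀ decrease" in *Lactobacillus* reads, "for the range of SD between 0.5 to 3" and "pre- and post-BSS use for type one error of 0.05". Table 1 has rows for N=20 and N=15. The sentence below it gives 87% power for 20 volunteers at SD 2, and calls the target a 2-fold change.

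The same section fixes the analysis: "for the primary endpoint, a paired t-test will be used to calculate the mean" log10 change at each post-treatment time point against baseline. Sections 4.1 and 4.2 describe one arm, each participant serving as their own comparator: "The study design is strengthened by comparing the microbiome within a same individual before and after intervention".

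Section 9.2 does not say which test underlies Table 1, whether alpha is one- or two-sided, whether the SD is that of a change or of a single visit, or what pre/post correlation is assumed.

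**The concern.** A paired test on 20 people and an unpaired test on two groups of 20 are different calculations. For the same SD entry, the paired noncentrality parameter is larger by a factor of √2, and the degrees of freedom are 19 instead of 38. If Table 1 was computed for the unpaired design, its powers do not describe the test the plan names.

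Table 1 is the only quantitative support for N=20. Section 9.2 expects more variability in humans than in mice, so the columns at SD 2 to 3 matter most to a reader, and the discrepancy is largest there.

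**Working it through.** **Inputs, all from section 9.2:** difference 2 on the log10 scale; SD 0.5 to 3; N=20 and N=15; alpha 0.05. I take alpha as two-sided, which is the choice that reproduces the table. Power is exact, from the noncentral t distribution.

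**Step 1: reproduce Table 1.** Two independent groups, N per group: df = 2N − 2, ncp = (2/SD)·√(N/2).
At N=20, SD 2: ncp = 1 × √10 = 3.162, df = 38, critical value 2.024, power 86.9%. The plan states 87%.

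| | SD 1.5 | SD 2 | SD 2.5 | SD 3 |
|---|---|---|---|---|
| N=20 per group, computed | 98.4 | 86.9 | 69.3 | 53.8 |
| N=20, stated | 98 | 87 | 69 | 54 |
| N=15 per group, computed | 94.1 | 75.3 | 56.2 | 42.2 |
| N=15, stated | 94 | 75 | 56 | 42 |

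All eight cells agree to the rounded percent. The cells at SD 0.5 and 1 sit at the ceiling (stated 100 and 99.9%) and do not discriminate between formulas.

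**Step 2: the named test, with SD as the SD of the within-person change.** Paired t: df = N − 1, ncp = (2/SD)·√N.
At N=20, SD 2: ncp = 1 × √20 = 4.472, df = 19, critical value 2.093, power 98.9%.

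| | SD 1.5 | SD 2 | SD 2.5 | SD 3 |
|---|---|---|---|---|
| N=20 paired | >99.9 | 98.9 | 92.4 | 80.7 |
| N=20, stated | 98 | 87 | 69 | 54 |
| N=15 paired | 99.8 | 94.9 | 82.1 | 67.1 |
| N=15, stated | 94 | 75 | 56 | 42 |

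The largest gap is at N=20, SD 3: 80.7 − 54 = 26.7 points. A one-sided paired test has still higher power and does not reproduce the table either.

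**Step 3: the alternative meaning of SD.** If SD is the SD at one visit and ρ the pre/post correlation, the SD of the change is SD·√(2(1 − ρ)).

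| | SD 1.5 | SD 2 | SD 2.5 | SD 3 |
|---|---|---|---|---|
| N=20, ρ=0 | 97.9 | 85.1 | 67.0 | 51.6 |
| N=15, ρ=0 | 92.4 | 72.2 | 53.2 | 39.8 |
| N=20, ρ=0.05 | 98.4 | 86.8 | 69.2 | 53.7 |
| N=15, ρ=0.05 | 93.6 | 74.3 | 55.3 | 41.5 |

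At ρ=0 the largest shortfall from the table is about 2.8 points (N=15, SD 2 and 2.5). At ρ=0.05 the N=20 row rounds to the stated figures, but the N=15 row rounds to 94/74/55/41. At ρ=0.06 the N=20, SD 2.5 cell becomes 69.7, which rounds to 70. On a grid of 0.0001, all eight cells round correctly only for ρ from 0.0553 to 0.0556. The two-sample formula matches them with no free parameter.

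**Step 4: the wording of the target.** A 2-log10 change is 100-fold. A 2-fold change is log10(2) = 0.301. With the paired test at N=20 and SD 2, ncp = (0.301/2)·√20 = 0.673 and power is about 10%.

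**The case against.** The strongest defence is that the SD might be a per-visit SD. Section 9.2 justifies its range by greater individual variability and lower abundance in humans, which could describe spread between people at one visit. On that reading Table 1 is numerically close to right for a paired test with almost no pre/post correlation. This stands in part: it makes the gap of up to 27 points conditional on SD being the SD of change. It does not rescue the table. The only SD given a source, 0.94, belongs to the pre/post reduction. A match requires an unstated correlation of about 0.055, and a value so near zero fits poorly with section 4.2, which counts within-person comparison as a strength.

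It is also fair to say that little hangs on the error. The study is an exploratory pilot, the planned analysis is correctly paired, and the understatement of power harms nobody. That stands, and it lowers the urgency.

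Three stronger inferences are tempting and are not supported:
- *The study is too small.* On the sourced meaning of SD the opposite holds for the 2-log10 target.
- *The plan accepts a fall to 15 participants.* N=15 is only a row of Table 1. Section 7.2 replaces those who leave before day 14, and the synopsis sets an accrual ceiling of 40.
- *The paired test removes every weak cell.* At N=15 and SD 3 its power is still only 67.1%.

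**Conclusion.** The inconsistency is real. The informative cells of "Table 1: Sample size and power calculation" belong to an unpaired comparison of 40 (or 30) independent people, a design this trial does not have.

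If SD is the SD of the within-person log10 change, the headline should be 98.9% and not 87%, and stated powers at SD 2 to 3 are too low by 12 to 27 points at N=20 and by 20 to 26 points at N=15. N=20 remains adequate for a 2-log10 change across the whole SD range shown (80.7% at SD 3). If SD is a per-visit SD, the table is off by at most about 3 points at zero correlation, but the plan omits the correlation needed to check it.

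This rests on two-sided alpha of 0.05, normally distributed log10 changes, the mouse SD being on the log10 scale, and complete pairs. The higher power applies only to a 2-log10 target; it gives no assurance about a 2-fold change, which is what the sentence under the table literally says. It is a correction to the sample-size section and should be made, but it does not call the design or the analysis into question.

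**What to change.** In section 9.2:
1. Recompute Table 1 with the paired (one-sample) t-test. For SD 1.5/2/2.5/3 the rows become >99.9/98.9/92.4/80.7% at N=20 and 99.8/94.9/82.1/67.1% at N=15; cells at SD 0.5 and 1 are about 100%.
2. State the test, that alpha is two-sided, and that SD is the SD of the within-person log10 change. If a per-visit SD is meant, give the assumed pre/post correlation and recompute on that basis.
3. Restate the headline: 20 participants give 98.9% power for a mean 2-log10 (100-fold) change if the SD of the change is 2, and 80.7% if it is 3. Replace the 2-fold wording.

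The cost is a recalculation and a few lines of text. The number of participants, the procedures and the planned analysis stay as they are.
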